10.3.1.2.2 Analysis Method

Absolute change in ppFEV₁ from baseline:

In the MMRM for the OLE efficacy period for Part A, the absolute change from baseline in ppFEV₁ will be analyzed using the MMRM approach based on the OLE-FAS for Part A. The model will include absolute change from baseline in ppFEV₁ as the dependent variable, and visit as the fixed effect, with baseline ppFEV₁ value and genotype group (F/F vs. F/MF) as covariates. The model will be estimated using restricted maximum likelihood. Denominator degrees of freedom for the *F*-test of fixed effects will be estimated using the Kenward-Roger approximation². An unstructured covariance structure will be used to model the within-subject errors. If the model estimation does not converge, a compound symmetry covariance structure will be used instead. Conditional on the observed data and covariates, missing data will be assumed to be missing at random; consequently, no imputation of missing data will be performed.

The estimated mean change from baseline in ppFEV₁ at each post-baseline visit, along with the corresponding 2-sided 95% confidence interval (CI) will be provided.

The analysis will be conducted with the clinic spirometry data only. An additional analysis may also be performed to include pooled spirometry data obtained in clinic and by Air Next Spirometer, if the Air Next Spirometry data are assessed to be reasonably consistent with clinic spirometry data.

Absolute change in sweat chloride from baseline:

Analysis of this PD variable will be based on an MMRM similar to the analysis of the absolute change in ppFEV₁ from baseline with the baseline sweat chloride included as a covariate instead of baseline ppFEV₁.

Absolute change in the CFQ-R respiratory domain score from baseline:

Analysis of this domain (child's version) will be based on an MMRM similar to the analysis of the absolute change in ppFEV₁ from baseline with the baseline CFQ-R respiratory domain score (child's version) included as a covariate instead of baseline ppFEV₁. The analysis will include clinic assessed CFQ-R RD score only. An additional analysis may be performed to include pooled CFQ-R RD score assessed at clinic and at home, if the home assessed data are reasonably consistent with the clinic assessed data.

Absolute change in BMI and BMI-for-age z-score from baseline:

Absolute change in weight and weight-for-age z-score from baseline:

Absolute change in height and height-for-age z-score from baseline:

Analysis of these variables will be based on an MMRM similar to the analysis of the absolute change in ppFEV₁ from baseline with the corresponding baseline included as a covariate instead of baseline ppFEV₁. The analysis will be conducted with clinic assessed data only. An additional analysis may be

performed to include data obtained in clinic and at home using the scales and stadiometers provided by Vertex, if the home assessed data are reasonably consistent with the clinic assessed data.

Number of PEx and CF-related hospitalizations:

The analysis of PEx will be based on Cumulative TC Set for Part A, and for the Cumulative TC Efficacy Period for Part A.

PEx will be summarized as described below:

- Number of events:
 - Number of PEx
 - Number of PEx requiring hospitalizations
 - Number of PEx requiring IV antibiotic therapy
 - Number of PEx requiring hospitalization or IV antibiotic therapy
- Duration of events:
 - Number of days with PEx
 - Number of days with PEx requiring hospitalizations
 - Number of days with PEx requiring IV antibiotic therapy
 - Number of days with PEx requiring hospitalization or IV antibiotic therapy

CF-related hospitalizations will be summarized as described below:

- Number of events:
 - Number of planned hospitalizations for CF (i.e., antibiotic therapy)
 - Number of unplanned hospitalizations for reasons other than antibiotic therapy for sinopulmonary signs/symptoms
- Duration of events:
 - Number of days of planned hospitalizations for CF (i.e., antibiotic therapy)
 - Number of days of unplanned hospitalizations for reasons other than antibiotic therapy for sinopulmonary signs/symptoms

For number of events variables, subjects with multiple defined events during the PEx analysis period will be counted multiple times. The annualized duration of events for each subject will be the total number of days with the defined events times 48 weeks divided by the total number of weeks on study up to the end of the PEx analysis period.

Absolute change in LCI_{2.5} from baseline:

Analysis of this variable will be based on an MMRM similar to the analysis of the absolute change in ppFEV₁ from baseline with the baseline LCI_{2.5} included as a covariate instead of baseline ppFEV₁.

For all continuous endpoints, to better assess the longitudinal profile of the efficacy and pharmacodynamics assessments with repeated measures up to OLE Week 96, the LS means (\pm SE) for absolute change from baseline at each visit will also be plotted. In addition, the post-baseline raw

values and the absolute change from baseline at each post-baseline visit will be summarized descriptively (n, mean, SD, median, minimum, and maximum).

10.3.1.2.3 Sensitivity Analysis

Not applicable because the primary endpoints are safety and tolerability assessments.

10.3.1.2.4 Analysis of Exploratory Efficacy Variables

Absolute change in FE-1 levels from baseline:

Summaries of observed values and change from baseline will be provided by visit. In addition, the number and percentage of subjects with shift changes from baseline (<15 mg/kg, \geq 15 mg/kg to <200 mg/kg, and \geq 200 mg/kg) at each post-baseline visit (<15 mg/kg, \geq 15 mg/kg to <200 mg/kg, and \geq 200 mg/kg) will also be provided.

Absolute change in serum levels of IRT from baseline:

Summaries of observed values and change from baseline will be provided by visit. In addition, the number and percentage of subjects with shift changes from baseline (<14ug/L, \geq 14ug/L to <40ug/L, and \geq 40ug/L) at each post-baseline visit (<14ug/L, \geq 14ug/L to <40ug/L, and \geq 40ug/L) will also be provided.

10.3.1.2.5 Analysis of Additional Efficacy Variables

Analysis of Additional Spirometry Variables

Summary statistics for raw values and for changes from baseline of the following spirometry measurements will be presented at each visit:

- FEV₁:
 - Absolute change from baseline in FEV₁ (L)
 - Relative change from baseline in FEV₁ (%)
 - Absolute change from baseline in percent predicted FEV₁ (percentage points)
 - Relative change from baseline in percent predicted FEV₁ (%)
- FVC:
 - Absolute change from baseline in FVC (L)
 - Relative change from baseline in FVC (%)
 - Absolute change from baseline in percent predicted FVC (percentage points)
 - Relative change from baseline in percent predicted FVC (%)
- FEF_{25-75%}:
 - Absolute change from baseline in FEF_{25-75%} (L/sec)
 - Relative change from baseline in FEF_{25-75%} (%)
 - Absolute change from baseline in percent predicted FEF_{25-75%} (percentage points)
 - Relative change from baseline in percent predicted FEF_{25-75%} (%)

- FEV₁/FVC:
 - Absolute change from baseline in FEV₁/FVC
 - Relative change from baseline in FEV₁/FVC (%)
 - Absolute change from baseline in percent predicted FEV₁/FVC (percentage points)
 - Relative change from baseline in percent predicted FEV₁/FVC (%)

Analysis of Other CFQ-R Variables

Summary statistics for raw values and for changes from baseline of the following CFQ-R domain scores will be presented at each visit.

- CFQ-R respiratory domain score (parent's version)
- CFQ-R non-respiratory domain score (child's version)
- CFQ-R non-respiratory domain score (parent's version)

Analysis of Additional LCI Parameters

Summary statistics for raw values and for changes from baseline of the following LCI parameters will be presented at each visit: LCI_{2.5}, LCI_{5.0}, and FRC.

10.3.2 Efficacy Analysis for the OLE study

All efficacy analyses described in this section will be based on the OLE-FAS, unless otherwise specified. The analysis will include all available measurements through the last scheduled visit in the OLE study, including measurements after treatment discontinuation.

Continuous endpoints during the parent study will be analyzed using the same mixed-effects model for repeated measures (MMRM) approach as described in the SAP for the parent study. The resulting estimates will be identical to what is available in the final CSR of the parent study. Similarly, continuous endpoints during the OLE efficacy period will also be analyzed using separate MMRM models for Parts A and B, so that Part A data will be analyzed consistently as what was done in the Part A analysis and the resulting estimates will be identical to the Part A analysis results. The results obtained from the parent study and the OLE efficacy period will be displayed one followed by the other.

There is no multiplicity adjustment.

10.3.2.1 Analysis of Primary Efficacy Variables

Not applicable.

10.3.2.2 Analysis of Secondary Efficacy Variables

10.3.2.2.1 Definition of Variables

The list of variables and their definitions are identical to Section 10.3.1.2.1

10.3.2.2.2 Analysis Method

Absolute change in ppFEV₁ from baseline:

For Part A data during the OLE efficacy period, the same model in Section 10.3.1.2.2 will be repeated. For Part B data during the OLE efficacy period, similar MMRM model will be applied based on the OLE-FAS. The model will include absolute change from baseline in ppFEV₁ as the dependent variable, and visit in Part B as the fixed effect, with baseline ppFEV₁ value and genotype group (F/F vs. F/MF) as covariates. The model will be estimated using restricted maximum likelihood. Denominator degrees of freedom for the *F*-test of fixed effects will be estimated using the Kenward-Roger approximation². An unstructured covariance structure will be used to model the within-subject errors. If the model estimation does not converge, a compound symmetry covariance structure will be used instead. Conditional on the observed data and covariates, missing data will be assumed to be missing at random; consequently, no imputation of missing data will be performed.

The estimated mean change from baseline in ppFEV₁ at each post-baseline visit, along with the corresponding 2-sided 95% confidence interval (CI) will be provided.

The analysis will be conducted with the clinic spirometry data only. An additional analysis may also be performed to include pooled spirometry data obtained in clinic and by Air Next Spirometer, if the Air Next Spirometry data are assessed to be reasonably consistent with clinic spirometry data.

Absolute change in sweat chloride from baseline:

Analysis of this PD variable will be based on an MMRM similar to the analysis of the absolute change in ppFEV₁ from baseline with the baseline sweat chloride included as a covariate instead of baseline ppFEV₁.

Absolute change in the CFQ-R respiratory domain score from baseline:

Analysis of this domain (child's version) will be based on an MMRM similar to the analysis of the absolute change in ppFEV₁ from baseline with the baseline CFQ-R respiratory domain score (child's version) included as a covariate instead of baseline ppFEV₁. The analysis will include clinic assessed CFQ-R RD score only. An additional analysis may be performed to include pooled CFQ-R RD score assessed at clinic and at home, if the home assessed data are reasonably consistent with the clinic assessed data.

Absolute change in BMI and BMI-for-age z-score from baseline;

Absolute change in weight and weight-for-age z-score from baseline;

Absolute change in height and height-for-age z-score from baseline:

Analysis of these variables will be based on an MMRM similar to the analysis of the absolute change in ppFEV₁ from baseline with the corresponding baseline included as a covariate instead of baseline ppFEV₁. The analysis will be conducted with clinic assessed data only. An additional analysis may be performed to include data obtained in clinic and at home using the scales and stadiometers provided by Vertex, if the home assessed data are reasonably consistent with the clinic assessed data.

Number of PEx and CF-related hospitalizations:

The analysis of PEx will be based on OLE Cumulative TC Set and for the OLE Cumulative TC Efficacy Period.

PEx will be summarized as described below:

- Number of events:

- Number of PEx
- Number of PEx requiring hospitalizations
- Number of PEx requiring IV antibiotic therapy
- Number of PEx requiring hospitalization or IV antibiotic therapy
- Duration of events:
 - Number of days with PEx
 - Number of days with PEx requiring hospitalizations
 - Number of days with PEx requiring IV antibiotic therapy
 - Number of days with PEx requiring hospitalization or IV antibiotic therapy

CF-related hospitalizations will be summarized as described below:

- Number of events:
 - Number of planned hospitalizations for CF (i.e., antibiotic therapy)
 - Number of unplanned hospitalizations for reasons other than antibiotic therapy for sinopulmonary signs/symptoms
- Duration of events:
 - Number of days of planned hospitalizations for CF (i.e., antibiotic therapy)
 - Number of days of unplanned hospitalizations for reasons other than antibiotic therapy for sinopulmonary signs/symptoms

For number of events variables, subjects with multiple defined events during the PEx analysis period (i.e., OLE Cumulative TC Efficacy Period) will be counted multiple times. The annualized duration of events for each subject will be the total number of days with the defined events times 48 weeks divided by the total number of weeks on study up to the end of the PEx analysis period.

Absolute change in LCI_{2.5} from baseline:

Analysis of this variable will be based on an MMRM similar to the analysis of the absolute change in ppFEV₁ from baseline with the baseline LCI_{2.5} included as a covariate instead of baseline ppFEV₁.

For all continuous endpoints, to better assess the longitudinal profile of the efficacy and pharmacodynamics assessments with repeated measures up to OLE Part B Week 96, the LS means (\pm SE) for absolute change from baseline at each visit will also be plotted. In addition, the post-baseline raw values and the absolute change from baseline at each post-baseline visit will be summarized descriptively (n, mean, SD, median, minimum, and maximum).

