7.2 Sample Size

The primary and secondary objectives of the study are the evaluation of the long-term safety, tolerability, and efficacy of ELX/TEZ/IVA. This is an open-label study that will enroll subjects who complete study treatment in the parent study and meet eligibility criteria. Sixty-four subjects enrolled in this open-label study.

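### If the unstructured MMRM fails, the only fallback is compound symmetry, which would give height and weight confidence intervals that are too narrow at the last visits if variance rises with time (conditional, minor)

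*SAP*

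**What the plan says.** The ppFEV₁ model is the template for all continuous endpoints. SAP 10.3.1.2.2 (Part A) and 10.3.2.2.2 (OLE study, Part B model) specify it in the same terms:

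- Covariance: "An unstructured covariance structure will be used to model the within-subject errors".
- Fallback: "If the model estimation does not converge, a compound symmetry covariance structure will be used instead". No heterogeneous structure and no robust standard error is named.
- Small-sample method: degrees of freedom for the test of "fixed effects will be estimated using the Kenward-Roger approximation".
- Output: the estimated mean change at each visit, "along with the corresponding 2-sided 95% confidence interval (CI) will be provided".
- Missing data: "missing data will be assumed to be missing at random; consequently, no imputation of missing data will be performed".

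BMI, weight, height and their z-scores take over this model with only the baseline term changed, "with the corresponding baseline included as a covariate instead of baseline ppFEV"₁. They therefore inherit the fallback. SAP 10.1 takes baseline before the first dose in the parent study. The sensitivity-analysis sections (10.3.1.2.3 and 10.3.2.2.3) are marked not applicable. SAP 7.2 reports the sample size: "Sixty-four subjects enrolled in this open-label study".

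**The concern.** Compound symmetry has two parameters: one variance and one correlation. Where the true variance of change differs by visit, the fitted variance is an average over visits, and every visit's interval is built from that average. If variance rises with follow-up, early intervals are too wide and late ones too narrow. Kenward-Roger adjusts for small samples within the assumed covariance and does not correct a wrong one. Under the missing-at-random assumption, the covariance also affects the estimated means once visits are missing.

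Raw height and weight are where a rise is most plausible. The parent study enrolled children aged 6 through 11, children grow at different rates, and change accumulates from before the parent study to Day 673 (Part A) or Day 1345 (Part B). The late visits carry the long-term message. The planned LS mean (± SE) plots would also show nearly equal error bars at all visits, at odds with the per-visit SDs in the descriptive tables.

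**Working it through.** The plan states no SD, power or coverage figure for these endpoints, so there is nothing to reproduce.

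**Inputs from the documents.** Target days for height and weight (SAP Tables 13-1 and 13-2):
- Part A, 9 visits: 57, 113, 169, 253, 337, 421, 505, 589, 673.
- Part B, 8 visits: 757, 841, 925, 1009, 1093, 1177, 1261, 1345.

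**Assumptions.** The lead-in from parent-study baseline is 24 weeks (168 days); the documents do not state the parent study's length. The SD of change is proportional to t^g, with t = target day + 168 and g = 0, 0.25, 0.5 or 1. Data are complete.

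**Covariance parameters, k(k+1)/2.** Part A: 9 × 10 / 2 = 45. Part B: 8 × 9 / 2 = 36. Compound symmetry: 2.

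**Formula.** With complete data, the compound-symmetry SE divided by the correct SE at visit t is r = √(mean of the visit variances) / SD at t. Coverage of the nominal 95% interval is 2Φ(1.96 r) − 1.

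**Part A** (t from 225 to 841):
- g = 1: mean of t² = 2,755,601 / 9 = 306,177.9, square root 553.3. Week 96: r = 553.3 / 841 = 0.66, coverage 80.3%. Week 8: r = 553.3 / 225 = 2.46.
- g = 0.5: mean of t = 4,629 / 9 = 514.3. Week 96: r = √(514.3 / 841) = 0.78, coverage 87.5%. Week 8: r = √(514.3 / 225) = 1.51.
- g = 0.25: mean of √t = 22.20. Week 96: r = √(22.20 / 29) = 0.875, coverage 91.4%. Week 8: r = √(22.20 / 15) = 1.22.

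**Part B** (t from 925 to 1513):
- g = 1: mean of t² = 12,184,040 / 8 = 1,523,005, square root 1,234.1. Week 96: r = 1,234.1 / 1,513 = 0.82, coverage 89.0%. Week 12: r = 1.33.
- g = 0.5: mean of t = 9,752 / 8 = 1,219. Week 96: r = √(1,219 / 1,513) = 0.90, coverage 92.1%. Week 12: r = 1.15.
- g = 0.25: mean of √t = 34.80. Week 96: r = √(34.80 / 38.90) = 0.95, coverage 93.6%. Week 12: r = 1.07.

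With g = 0, coverage is 95% at every visit.

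**A concrete height model (assumption).** Growth is 6 cm/year with between-child SD 1 cm/year, and measurement error is 0.5 cm at baseline and at each visit. The variance of change is (t/365.25)² + 0.25 + 0.25. In Part A this is 0.879 at Week 8, 5.802 at Week 96 and 2.795 on average. Week 8: r = √(2.795 / 0.879) = 1.8. Week 96: r = √(2.795 / 5.802) = 0.69, coverage about 83%. If the baseline covariate absorbs the baseline error, Week 96 coverage is about 82%. In Part B, Week 96 coverage is about 89%. With 64 subjects, the Part A Week 96 half-width would be 1.96 × √(2.795 / 64) = 0.41 cm instead of 1.96 × √(5.802 / 64) = 0.59 cm, around a mean change of 6 × 841 / 365.25 = 13.8 cm.

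**Simulation.** In 400 runs (64 subjects, random slopes plus noise, 10% dropout, 24-week lead-in), compound symmetry was fitted by REML with t limits on n − 3 degrees of freedom, not full Kenward-Roger. Coverage was 72.8% at Part A Week 96 and 89.0% at Part B Week 96. Intervals using each visit's own variance gave 94.2% and 95.0%. The Part A result is lower than the formula's 80.3% by more than its Monte Carlo error, √(0.728 × 0.272 / 400) = 2.2 points. The size stated in this point therefore rests on the formula, not on that run.

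**Does the unstructured fit fail?** Fits to simulated data (9 visits, 64 subjects, about 15% dropout and 10% intermittent missing) failed in 0 of 100 runs. Under the height model they failed in 0 of 60. Both used maximum likelihood by EM, not the planned REML fit in SAS.

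**The case against.** The strongest objection is that the fallback may never be used. Forty-five parameters for 64 subjects sounds thin, but 9 × 64 = 576 observations are possible, and the convergence checks found no failure. A reader might infer that growth endpoints are the ones most likely to fail because serial heights are nearly collinear. Nothing in the documents or the checks shows this. The checks are not the planned fit, so failure is not excluded.

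A reader might also be drawn to larger figures. With no lead-in and SD proportional to time, the Part A Week 8 standard error is about 7 times too large, and Week 96 coverage falls to 75.8%. That input contradicts SAP 10.1: baseline precedes the first parent-study dose, so time has already elapsed at Part A Day 1. Even the 2.5-fold figure needs an SD exactly proportional to time with no measurement error; the height model gives about 1.8.

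Rising variance is itself an assumption. It is not shown for the three z-scores, which are adjusted for age and sex, and without a rise the problem disappears. Finally, these are secondary endpoints with no hypothesis test or decision rule. SAP 10.3.1.2.2 and 10.3.2.2.2 report n, mean and SD of change at each visit in any case, so a reader could form a visit-specific interval.

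All of this limits the point. It does not remove it: the SAP commits to a 95% interval at each visit and prescribes what to do on failure, and that prescription is poor for endpoints whose variance rises.

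**Conclusion.** The point holds conditionally and is minor. If the unstructured fit fails and the variance of raw height or weight change rises with time, the prescribed fallback gives nominal 95% intervals with coverage of about 80–91% at Part A Week 96 and 89–94% at Part B Week 96, and a Part A Week 8 standard error about 1.2 to 2.5 times too large. These ranges assume a 24-week lead-in, complete data and SD growth between time^0.25 and time^1. A longer lead-in would shrink the error and a shorter one would enlarge it. The effect at the study's final visit, Part B Week 96, is moderate. The documents do not support saying that the growth intervals will be wrong, that the fallback is likely to be needed, or that the z-scores are affected.

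**What to change.** In SAP 10.3.1.2.2 and 10.3.2.2.2, replace the fallback sentence with an ordered list: heterogeneous Toeplitz, then heterogeneous AR(1), then heterogeneous compound symmetry. Use the first that converges, with Kenward-Roger. Allow homogeneous compound symmetry only if all three fail, and then with an empirical (sandwich) standard error. State in the report which structure was used for each endpoint.

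The cost is one sentence in two sections and a few more covariance parameters when the fallback is used. Nothing changes if the unstructured model converges. SAP 10.3.2 requires Part A estimates in the final analysis to match those of the Part A analysis. The sponsor should therefore check whether compound symmetry was already used for any Part A endpoint. If so, keep that result and report the heterogeneous fit beside it.
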